## 2.3 Data Conventions

The data conventions and definitions listed in this section are to be applied to all analyses unless stated otherwise in a subsequent section of this Analysis Plan.

- Data will be analyzed according to the 3 treatment groups, ie, (1) BOTOX 8 U/kg, (2) BOTOX 4 U/kg, and (3) Placebo.
- Concomitant medication and prior medication will be calculated using the following convention: 1) If the stop date of taking medication is prior to injection date, then it will be counted as prior medication; 2) If the start date of taking medication is after or on injection date, then it will be counted as concomitant medication; 3) If the start date of taking medication is prior to injection date and stop date is on or after injection date, then it will be counted as both prior medication and concomitant medication.
- Concurrent procedures are defined as those taken on or after the first injection date.
- All data will be listed with the exceptions of commonly expected results such as physical examination, pregnancy tests results for females when not applicable, etc.
- The level of significance used for all statistical tests will be 0.05. All hypotheses will be tested for statistical significance with 2-sided alternatives.

- Summary statistics of continuous variables will include the sample size (N), mean, standard deviation, median, minimum (Min), and maximum (Max).
- Summary statistics of categorical variables will include the sample size (N) and/or frequency counts and percentages.
- Medical Dictionary for Regulatory Activities (MedDRA) nomenclature will be used to code all adverse events and medical history.
- World Health Organization Drug Dictionary Enhanced (WHO DDE) preferred name and MedDRA will be used to code all medications.
- Metric systems will be used for all applicable measures including (kg), height (cm), and clinical laboratory data (SI: Standard International units).
- Unless otherwise defined, baseline will be the last non-missing value of an analysis variable before treatment. Therefore, in general values collected prior to the treatment on day 1 will be used as baseline except for clinical laboratory tests which will be performed at screening instead of day 1. In the event a variable value is missing at the day 1 before treatment time point, the last non-missing value before day 1 will be used as baseline. Change from baseline is calculated as follow-up minus baseline value.
- Missing values will not be imputed. The multiple imputation (MI) method is only intended for sensitivity analyses of MAS-B ankle scores with knee extended and CGI by Physician.
- Study days from randomization/day 1 will be calculated as:  

$$\text{Study days} = \text{visit date} - \text{randomization/day 1 visit date} + 1.$$
- The study day of an event that has occurred before randomization/day 1 will be calculated as:  

$$\text{Study day} = \text{date of event} - \text{randomization/day 1 visit date}.$$
- Partial dates occurring when calculation of study day is germane to the study outcome will be handled as follows:  
If the year is missing then the date is treated as missing.

If either the month or the day is missing, then the closest date to baseline possible will be used. That is, an event occurring the year before baseline would use December and/or the last day of the month. An event occurring the year after baseline would use January and/or the first day of the month.

All partial dates will be listed “as is” in the data listings.

- All adverse events with missing onset dates will be identified and the missing dates will be imputed as follows for analysis. These imputations are only for assigning adverse events to a particular study phase; calculations such as days to onset will not use these imputations. All partial dates will be listed “as is” in the data listings.
  - (a) For adverse event onset date: If day and month are missing but year is available (..../yy) then the imputed day and month will be 01/01/yy or the injection date if they have the same year, whichever is later. If the day is missing but the month and year are available (mm/../yy), then the imputed day will be mm/01/yy or the injection date if they have the same month and year, whichever is later.
  - (b) For adverse event stop dates: If day and month are missing but year is available (..../yy) then the imputed day and month will be 12/31/yy or the study exit date if they have the same year, whichever is earlier. If day is missing but the month and year are available (mm/../yy), then the imputed day will be the last day of the month mm in the year yy or the study exit date if they have the same month and year, whichever is earlier.
  - (c) If the adverse event onset or stop month, day, and year are missing (..../..), then the study entry date will be used as the adverse event onset date and the exit date will be used as the adverse event stop date.
- Data from unscheduled visits or re-test visits will be treated the same way as scheduled visits, ie, the dates of such visits will be used in the categorization of visit window. The algorithm handling multiple visits within a visit window will also be applied to unscheduled visits and re-test visits.
- For the primary and secondary efficacy analyses where study center is a factor in the analysis model, centers that recruited only a few patients will be pooled together. The following algorithm for pooling study centers will be used:
  - A. Pooling of study centers will by country.
  - B. Within each country, the following will be conducted:

1. Study centers will be ranked in descending order of the total number of patients enrolled.
2. Any center with at least 12 patients will stand on its own.
3. The first center with fewer than 12 patients will be combined with the next center until the total number in the pooled center reaches or exceeds 12 patients.
4. The algorithm of combining centers will continue down the list as described above.
5. If the last pooled center still has less than 12 patients, the last pooled center will be combined with the previous pooled center.

C. If there are less than 12 subjects enrolled in a country, the country will be pooled to the smallest center in the same region (alphabetical order if there is a tie). The regions include Asia-Pacific, Europe, and North America. For example, if Canada enrolled less than 12 patients, Canada will be pooled with a smallest center in the United States.

- The mean change from baseline for a given treatment group will be calculated by taking the sum of all individual changes from baseline divided by the number of patients with observations in that treatment group. As a consequence, patients without the particular follow-up data will not be taken into account, except if there is a missing value replacement method used.

|

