7.5 Sample Size Calculation

Approximately 412 patients will be enrolled to ensure that at least 351 patients (117 per treatment group) will complete the study.

Using a 2-sample t-test, a significance level of 0.05, and the assumptions in Table 4, the power for MAS-B change from baseline is 94% (PASS, Hintze, 2008). The calculation is based on assumptions for 8 U/kg group and placebo group. Since there are 2 co-primary endpoints for the US FDA analysis, for 8 U/kg group the power for CGI by Physician is calculated to be 97%, and the overall power for the US FDA co-primary endpoints will be at least 91%. The assumptions for MAS-B were based on results of completed Studies BTX108509 and BTX108512; the estimates for CGI were based on results of completed Study 191622-021.

Table 4 **Sample Size Assumptions and Power Calculations**

Endpoint	Average of Week 4 and 6 for 8 U/kg group	Average of Week 4 and 6 for Placebo group	Standard Deviation	Power
MAS-B Change from Baseline	-0.8	-0.45	0.75	94%
CGI by Physician (Co-primary for US FDA Analysis)	1.2	0.6	1.2	97%
Overall Endpoints				91%

CGI = Clinical Global Impression of Overall Change; MAS-B = Modified Ashworth Scale – Bohannon; US FDA = United States Food and Drug Administration

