## **1.2 Secondary and Other Objectives**

There are no secondary or other objectives for this study.

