## 5.2 Primary Efficacy Analyses

### 5.2.1 Primary Analyses of Primary Efficacy Variable

The primary efficacy analyses will be based on the mITT population. The primary analysis will be conducted for the average of change from baseline in MAS-B of the ankle plantar flexors with

knee extended at weeks 4 and 6. For the assessment of treatment groups in the primary endpoint, the statistical null hypothesis is that both BOTOX higher dose (8 U/kg) and lower dose (4 U/kg) have the same mean as placebo. The alternative hypothesis is that at least one study dose of BOTOX has a different mean than placebo. The hypothesis will be tested using Mixed Model Repeated Measures (MMRM) at significance level of 0.05. The primary variable will be summarized by treatment group. The differences of each BOTOX dose group and the placebo group will be used to test the null hypothesis. The analysis will include weeks 2, 4, 6, 8, 12 data. The model will include baseline MAS-B ankle score with knee extended as a covariate and factors of age group, treatment group, visit, treatment-by-visit interaction, study center and previous botulinum toxin exposure. Age group is represented by stratification categories ( $\leq 6$  years and  $> 6$  years). Baseline MAS-B ankle score with knee extended is a continuous variable included as a covariate. Pooled study center will be produced to ensure each contains at least 12 patients. Pooling method is described in Section 2.3.

A gate-keeping approach will be used to control the type I error rate for the primary endpoint. Specifically, 8 U/kg versus placebo will be tested first followed by the 4 U/kg versus placebo comparison, each at 2-sided 0.05 level. The 4 U/kg versus placebo comparison will only be performed if the test for 8 U/kg versus placebo is statistically significant.

The co-primary analyses for US FDA only is described in Section 10.

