## **5.3 Secondary Efficacy Analyses**

For secondary efficacy analyses, the observed cases will be used unless stated otherwise.

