### **5.3.1 CGI by Physician**

CGI by Physician will be rated at study weeks 2, 4, 6, 8, and 12. Descriptive statistics will be presented by treatment group at each assessment timepoint and for the average of weeks 4 and 6. CGI by Physician will be summarized and analyzed by MMRM, as well as ANCOVA at each assessment timepoint using observed cases. MMRM model will include baseline MAS-B ankle score with knee extended as a covariate and factors of age group, treatment group, visit, treatment-by-visit interaction, study center and previous botulinum toxin exposure. The frequency distribution of the CGI scores, as well as the percentage of responders (CGI score  $\geq 1$ ), will be summarized by treatment group at each post-treatment visit. A logistic regression analysis will also be performed on the responder status at each post-treatment visit with factors of age group, treatment group, study center, and previous botulinum toxin exposure, if applicable.

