### 10.1               **Primary Efficacy Analyses**

There are 2 co-primary endpoints: the average grade change from baseline in the MAS-B ankle score with knee extended at weeks 4 and 6 and the average CGI by Physician at weeks 4 and 6. For both co-primary endpoints, the statistical null hypothesis is that both the higher dose (8 U/kg) and the lower dose (4 U/kg) have the same mean as placebo. The alternative hypothesis is that at least one study dose has a different mean than placebo. In addition to the primary statistical analyses cited in Section 5.2.1 for the average grade change from baseline in MAS-B ankle score with knee extended at weeks 4 and 6, the average CGI by Physician at weeks 4 and 6 will be analyzed using the same statistical method with a same MMRM model in Section 5.3.1.

The Hochberg procedure (Hochberg and Tamhane, 1987) will be used to control the family-wise type I error rate. With 2 doses and 2 co-primary endpoints in each dose, the maximum p-value for the 2 co-primary endpoints in each dose will be used in the Hochberg procedure. We first define the following values:

p11: p value for Botox 8 U/kg vs placebo comparing MAS-B

p12: p value for Botox 4 U/kg vs placebo comparing MAS-B

p21: p value for Botox 8 U/kg vs placebo comparing CGI

p22: p value for Botox 4 U/kg vs placebo comparing CGI

$p1 = \max(p11, p21)$ ,  $p2 = \max(p12, p22)$ .

$p_1$  and  $p_2$  will be sorted in an increasing order to get  $p(1) \leq p(2)$ . The following decision rule will then be applied:

Step 1: If  $p(2) \leq 0.05$ , both doses are considered efficacious; otherwise go to step 2.

Step 2: If  $p(1) \leq 0.025$ , its corresponding dose is considered efficacious; otherwise go to step 3.

Step 3: Neither dose is considered efficacious.

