## **10.2 Secondary Efficacy Analyses**

The secondary efficacy analyses will be the same as the statistical analyses cited in Section 5.3 except for the analyses for CGI by Physician which is described in the Section 10.1.

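### Does the plan need a rule for reading the secondary efficacy p-values, given that CGI at weeks 4 and 6 is under Hochberg control in the US analysis but tested at 0.05 per dose elsewhere?

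*SAP*

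**What the plan says.** The general convention in SAP 2.3 is "The level of significance used for all statistical tests will be 0.05", two-sided, unless a later section says otherwise. The Protocol Summary sets the same level for all tests.

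Two later sections add error control:

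- **Non-US, MAS-B only.** SAP 5.2.1 tests 8 U/kg first: "The 4 U/kg versus placebo comparison will only be performed if the test for 8 U/kg versus placebo is statistically significant". Protocol 7.3.1 likewise confines the gate to the MAS-B endpoint.
- **US, MAS-B and CGI as co-primaries.** SAP 10.1 and Protocol 7.7.1 take the larger of the MAS-B and CGI p-values within each dose and apply Hochberg across the two doses. The CGI average "will be analyzed using the same statistical method with a same MMRM model in Section 5.3.1".

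For the secondary endpoints, SAP 5.3 opens with "For secondary efficacy analyses, the observed cases will be used unless stated otherwise". Sections 5.3.1 to 5.3.3 then give the models. For CGI: "CGI by Physician will be summarized and analyzed by MMRM, as well as ANCOVA at each assessment timepoint using observed cases". These sections give no order, no split of the significance level and no link to the MAS-B gate. Protocol 7.3.2 is equally silent. In the US analysis, "The secondary efficacy analyses will be the same as the statistical analyses cited in Section 5.3 except for the analyses for CGI by Physician", so GAS and MTS are treated there as in SAP 5.3. SAP 1.2 states: "There are no secondary or other objectives for this study".

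**The concern.** The same CGI model yields the same two dose-versus-placebo p-values in both analyses, yet they seem to be held to different standards. In the US analysis a CGI result counts only through the per-dose maximum under Hochberg. In the non-US analysis each dose is compared with 0.05 and no gate applies.

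A second asymmetry lies within the non-US analysis. If MAS-B at 8 U/kg fails, MAS-B at 4 U/kg is not tested, while CGI, GAS and MTS at 4 U/kg still are.

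Read literally, SAP 2.3 would let a report call any of these secondary results statistically significant. That could happen at a dose for which MAS-B cannot be claimed, or which the US rule does not declare efficacious. What is at stake is the family-wise error of the secondary claims and the wording of the report.

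**Working it through.** **Inputs.** Protocol 7.5 and Table 4 give 117 per group, a two-sample t-test at 0.05, MAS-B −0.8 against −0.45 (difference 0.35, SD 0.75), and CGI 1.2 against 0.6 (difference 0.6, SD 1.2). On these inputs, "The calculation is based on assumptions for 8 U/kg group and placebo group", so the effect at 4 U/kg is not given. It is assumed below to be 50%, 75% or 100% of the 8 U/kg effect. The MAS-B/CGI correlation is not given either and is varied. The checks below use normal approximations.

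**1. Reproduce the plan's power.** The standardised effect is difference / (SD × √(2/117)), with √(2/117) = 0.1307.

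- MAS-B: 0.35 / (0.75 × 0.1307) = 3.57. Power is 94.6% (94.5% by noncentral t), against 94% stated.
- CGI: 0.6 / (1.2 × 0.1307) = 3.82. Power is 96.9% (96.8% by noncentral t), against 97% stated.
- Both endpoints: 0.945 × 0.968 = 0.914, against at least 91% stated.

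The sizing stands and is untouched by this point.

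**2. Non-US CGI, no effect at either dose.** With 1:1:1 allocation each contrast has variance 2σ²/n, and the shared placebo group gives covariance σ²/n, so the correlation is 0.5. The chance of at least one p ≤ 0.05 is 1 − P(|Z₈| ≤ 1.96 and |Z₄| ≤ 1.96) = 9.1% (bivariate normal). Independence would give 1 − 0.95² = 9.75%.

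**3. US rule, same CGI null.** MAS-B is set at its Table 4 effect at both doses (an assumption). The full rule is simulated in 2 million trials per setting: per-dose maximum, then the 0.05 and 0.025 steps.

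| MAS-B/CGI correlation | False claim for at least one dose |
|---|---|
| 0 | 4.4% |
| 0.3 | 4.1% |
| 0.5 | 3.7% |
| 0.6 | 3.4% |

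Hochberg applied to the two CGI p-values alone would give 4.8%, but that is not the plan's rule, because MAS-B must also pass.

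**4. CGI at 4 U/kg reaches 0.05 while the MAS-B gate at 8 U/kg fails.** Both endpoints have their Table 4 effects at 8 U/kg.

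| 4 U/kg effect, as share of 8 U/kg | Correlation 0 | Correlation 0.5 |
|---|---|---|
| 50% | 2.6% | 1.5% |
| 75% | 4.4% | 3.5% |
| 100% | 5.2% | 4.9% |

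A wider count includes every trial in which CGI at 4 U/kg reaches 0.05 and MAS-B at 4 U/kg is not claimable for any reason. It gives 27.6%, 21.0% and 9.1% at correlation 0, and 19.5%, 16.2% and 8.3% at 0.5. The excess comes from trials where MAS-B passes at 8 U/kg and simply misses 0.05 at 4 U/kg. At the 50% effect and correlation 0 that is 27.6 − 2.6 = 25.0 points. This is ordinary disagreement between two endpoints, and the gate has no part in it. Since CGI truly has an effect in these scenarios, none of these figures is a false-positive rate.

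**5. Set the hypotheses beside the controls.**

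| Analysis | Hypothesised endpoints (Protocol 2.2, 7.2.1) | Control |
|---|---|---|
| Non-US | MAS-B | Fixed sequence, 8 then 4 U/kg |
| US | MAS-B and CGI | Per-dose maximum, Hochberg over doses |

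Each hypothesised endpoint is controlled in the analysis that hypothesises it. MAS-B itself is handled differently in the two analyses, so the difference for CGI is part of a deliberate two-track design.

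**The case for a change.** The strongest case for a change is that SAP 2.3 is an explicit default that SAP 5.3 and 10.2 never override. The secondary programme is also large. The tests in SAP 5.3.1 to 5.3.3 can be counted as 22 for CGI (2 + 10 + 10), 24 for GAS (8 + 16) and 120 for MTS (60 + 60), 166 in all. If every null were true, 166 × 0.05 = 8.3 would be expected to reach 0.05. The sponsor wrote a reading rule for MAS-B and none for the rest. A sentence calling the remaining p-values nominal would be cheap and is best written before unblinding.

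The silence is real, and so is the lack of family-wise control over the secondary tests. But the scope of control can be read from the plan: the gate is stated for the primary endpoint, Hochberg for the co-primaries, and SAP 1.2 disclaims secondary objectives. A statistician writing the report would treat the other p-values as unadjusted and supportive. The comparison between regions also sets unlike outputs side by side. The US rule declares a dose efficacious on both endpoints and gives no separate CGI verdict.

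A formal order would not be a free improvement. At correlation 0.3, testing MAS-B 8, MAS-B 4, then CGI 8 U/kg would allow a CGI claim at 8 U/kg in about 42%, 73% or 88% of trials for 4 U/kg effects of 50%, 75% or 100%. Placing CGI 8 U/kg second would raise that to about 92%, but would lower the chance of claiming MAS-B at 4 U/kg from 42.6%, 74.4% and 90.6% to 41.7%, 72.5% and 88.2%.

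**Conclusion.** The plan lacks one sentence of interpretation, and its error control is sound for what it sets out to claim. The non-US gate and the US Hochberg rule cover every hypothesised endpoint, and their results do not depend on how secondary p-values are described. The uncontrolled family-wise rate for the two non-US CGI tests is about 9.1% under a CGI null, against 3.4% to 4.4% for a false dose claim under the US rule. The gate-specific conflict at 4 U/kg would arise in about 1.5% to 5.2% of trials. The US range and the conflict figures rest on assumed correlations (0 to 0.6 and 0 to 0.5 respectively). The US range also assumes the planned MAS-B effect at both doses, and the conflict figures assume 4 U/kg effects of 50% to 100% of those at 8 U/kg.

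This is a gap that analysts fill sensibly by reporting the secondary p-values as unadjusted. Writing that down would be harmless but would change no estimate, test or sample size. Imposing a testing order would exchange power between endpoints without serving any stated hypothesis. No change to the plan is needed.

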8.2 Procedures for Final Study Entry

At visit 3 (randomization) patients must meet all of the inclusion criteria and must not meet any of the exclusion criteria. Also, all females of childbearing potential must have a negative urine pregnancy test.

The patient is considered to have entered this study at the time of randomization to treatment on day 1. See Section 5.5 for the method for assignment to treatment groups/randomization.

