## 4.6 Pre-treatment Adverse Events

Data for pre-treatment adverse events, adverse events with onset date in-between informed consent date and randomization/day 1 visit or medical history that worsened duration this period will be listed.

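### The rule for missing adverse event onset dates ignores the stop date, so an event known to have ended before injection can be dated to the injection day

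*SAP*

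**What the plan says.** SAP 2.3 (Data Conventions) imputes missing adverse event onset dates in three cases.

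- Day missing, month and year known: "then the imputed day will be mm/01/yy or the injection date if they have the same month and year, whichever is later".
- Day and month missing, year known: "then the imputed day and month will be 01/01/yy or the injection date if they have the same year, whichever is later".
- Date fully missing: "then the study entry date will be used as the adverse event onset date". The SAP does not define study entry. Protocol 8.2 does: "The patient is considered to have entered this study at the time of randomization to treatment on day 1".

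The purpose is narrow: "These imputations are only for assigning adverse events to a particular study phase". Time to onset does not use the imputed dates, and partial dates are listed as recorded.

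Pre-treatment events are defined in SAP 4.6 as "adverse events with onset date in-between informed consent date and randomization/day 1 visit", or medical history that worsened in that period, and they are only listed. SAP 6.2 defines a treatment-emergent event by onset after treatment has begun, or by earlier onset with worsening or new seriousness afterwards. Treatment-emergent events are tabulated by arm, and possible distant spread of toxin is assessed with a list of 39 preferred terms.

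**The concern.** Adverse events are recorded from informed consent (Protocol 9.1.1), and screening takes place 2 to 4 weeks before day 1 (Protocol 8.3.1). Events that start and end before injection will therefore be in the database. For these the stop date alone settles the phase. The onset rules never look at it, and neither the treatment-emergent nor the pre-treatment definition makes an exception for an event that was over before injection.

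The imputation exists only to assign phase, so an event whose phase is already known can be assigned to the wrong one. It would then move from a listing into the by-arm incidence tables. The distant-spread list includes ordinary childhood complaints such as constipation, as well as dyspnoea. In a small table, one misplaced event would be noticed.

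The SAP already uses the appropriate logic for medications: in the same section, a drug stopped before the injection date is classed as prior medication. A drug given for a screening event could thus be classed as prior while the event itself is classed as post-treatment.

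**Working it through.** The plan gives no figure to reproduce. The check is to apply the rule as written, then size it under stated assumptions.

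**1. What the rule returns.** If the onset month and year match the injection, the imputed onset is max(first of the month, injection date). The first of the month is never after the injection, so the result is the injection date exactly. The same holds for 1 January when only the year is known. If only the day is missing and the onset month precedes the injection month, the result is the first of that earlier month and the event stays pre-treatment.

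**2. Example (assumed dates).** Onset May with day missing, stop 8 May, injection 20 May. Imputed onset = max(1 May, 20 May) = 20 May, and 20 − 8 = 12 days after the event ended.

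**3. Fully missing onset.** Study entry is randomization on day 1, normally the injection day, so a known earlier stop date is ignored here too.

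**4. Share of events affected, day missing.** Assumptions, none of them from the documents except the length of screening:

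- L, days from onset to injection, is uniform on 1 to W, with W = 28, 21 or 14.
- D, the injection's day of the month, is uniform on 1 to 30.
- Each event lasts a fixed d days, so stop = onset + d.

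Onset falls in the injection month if D > L, with probability (30 − L)/30. The event is over before injection if L > d. The share meeting both conditions is

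Σ (30 − L) / (30·W), summed over L = d + 1 to W.

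| Duration | W = 28 | W = 21 | W = 14 |
|---|---|---|---|
| Same month, ended or not | 434/840 = 51.7% | 399/630 = 63.3% | 315/420 = 75.0% |
| 7 days | 252/840 = 30.0% | 217/630 = 34.4% | 133/420 = 31.7% |
| 14 days | 119/840 = 14.2% | 84/630 = 13.3% | 0 |
| 21 days | 35/840 = 4.2% | 0 | 0 |

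Applying the rule to every injection date in a four-year calendar gives 52%, 64% and 75% for the first row. In that run no onset was moved past the injection date. All of these are shares of pre-injection events with a missing onset day, not of all adverse events.

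**5. Effect on comparisons.** If a fraction q of patients in every arm gains a spurious event, an incidence p becomes p + q(1 − p), and a risk difference is multiplied by (1 − q). Illustration with assumed incidences of 10% and 5%:

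- q = 1%: 10.9% and 5.95%. The difference is 4.95 points instead of 5.00; the ratio is 1.83 instead of 2.00.
- q = 0.1%: 10.09% and 5.095%. The ratio is 1.98.

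**The case against.** Assigning an uncertain onset to the treatment phase is a standard conservative convention. It over-counts and does not hide events, and it applies alike to all arms. The adverse event tables are descriptive, with no test specified. Partial dates are listed as recorded, so a stop date before injection would be visible in the listings. Sites query for events at screening and again before treatment on day 1, so a dated stop with only a year, or nothing, for onset should be very rare in a window of at most four weeks. All of this stands and keeps the point small. It does not justify the rule where the stop date removes the uncertainty.

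Four stronger readings are tempting and are not supported.

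- A reader might infer that onsets are pushed beyond the injection date. They are set to that date exactly.
- A reader might take the 52% same-month share as the error rate. It includes events still ongoing at injection, for which the present rule is reasonable.
- A reader might conclude that real differences between BOTOX and placebo would be diluted. Ratios move toward 1, but risk differences hardly change at a plausible q.
- A reader might say that rule (c) replaces a known stop date with the exit date. Its wording allows that, but the introductory sentence speaks of imputing the missing dates, so this is one reading of unclear text.

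It is also fair to say that entry into the treatment-emergent tables is not explicit. SAP 6.2 requires onset after treatment starts, and an onset imputed to the injection day is not plainly after it. Post-treatment is the natural reading of a rule that picks the later date in order to assign phase. On the opposite reading, the conservative convention would fail for the uncertain events it is meant to catch. Either way the SAP should say which applies.

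**Conclusion.** The point holds in a limited form and is minor. The rule gives a wrong phase for events that have a partial or missing onset date falling under SAP 2.3(a) or (c) and a stop date known to precede injection. For these it produces an onset later than the event's own end.

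With a missing onset day and a 28-day window, about 30%, 14% or 4% of pre-injection events would be affected for durations of 7, 14 or 21 days. This rests on the uniform-onset, 30-day-month and fixed-duration assumptions, and on an onset imputed to the injection day counting as treatment-emergent. The documents do not say how many partial onset dates to expect; the number is probably small. The consequence is slightly inflated incidence in all arms and ratios pulled a little toward 1, with little change in risk differences and none in efficacy.

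**What to change.** In SAP 2.3(a) and (c), make three changes.

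1. Add that an event whose stop date precedes the injection date is pre-treatment, and that its imputed onset may not be later than the stop date. The stop date may be complete, or partial if it is unambiguous (for example, a stop month before the injection month).
2. Keep the present rule for events that are ongoing or have no informative stop date, and state that an onset imputed to the injection date under that rule counts as treatment-emergent.
3. Word (c) so that only the date that is missing is imputed.

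The cost is a few sentences in the SAP and one condition in the program, with no new data. It should be settled before unblinding, so that no safety event is reclassified with treatment known.
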